11.1.6.4. Incidence of surgically harvested donor site wounds

This is a counting variable, giving the number of donor site wounds per patient. Rates of patients with different numbers of donor site wounds will be analyzed by displaying counts and percentages by treatment group. The number of donor site wounds will be compared between treatment groups using a chi square test (or Fisher's exact test in case of small estimated cell counts).

11.1.6.5. % area of surgically harvested donor site wounds

The % wound area of surgically harvested donor site wounds per patient (computed as in section 10.3.5.5) will be presented by treatment group using descriptive statistics and compared between groups with a one-way analysis of variance.

11.1.6.6. Blood loss using changes in hemoglobin following eschar removal procedures

The measure of blood loss defined in Section 10.3.5.6 will be computed for each patient, presented by treatment group using descriptive statistics and compared between groups with a one-way analysis of variance.

11.1.6.7. POSAS

The POSAS will be evaluated on a subject level. The POSAS based on target wounds will be calculated as outlined in Section 10.3.5.7 and will be presented by treatment group using descriptive statistics. The mean POSAS values between treatment groups will be compared by a one-way analysis of variance.

The analysis will be repeated for the patient scale and for the observer scale separately.

The analyses will be conducted for the POSAS assessments (both on-site and remotely collected) of 6 and 12 weeks and 6 and 12 months.

In addition, the analysis will be repeated excluding subjects with remotely collected data.

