- 4. Reduction in surgical need as measured by analysis of incidence of surgically harvested donor sites scars,
- 5. Reduction in surgical need as measured by analysis of % area of surgically harvested donor site scars.
- 6. Blood loss related to eschar removal assessed by changes in Hemoglobin incurred during the eschar removal procedures
- 7. PK evaluation in NexoBrid patients
- 8. Cosmesis and Function: Demonstrate non-inferiority to SOC in quality of scars of burns using POSAS treated with NexoBrid, measured at 12 months from wound closure,
- 9. Cosmesis and Function: Demonstrate non-inferiority to SOC in quality of scars of burns using POSAS treated with NexoBrid, measured at 24 months from wound closure,

Protocol: MW 2012-01-01	Version 11.01- 16 Jun 2021	Page 8 of 10

	10. Duration of hospitalization.
	Primary Endpoints
	The following primary endpoint will be evaluated in this study at a 'per patient' level:
	1. Earlier eschar removal- Analysis will be based on the time from the date of randomization. NexoBrid will be compared with SOC using Cox regression analysis. Kaplan-Meier curves will be presented graphically to display the distribution of time to complete eschar removal under the two treatments.
	Subgroup analyses are based on the following: Age groups (Comparison of 0-23 months; 24 months-3 years; 4-11 years; 12-18 years).
	Safety
Statistical Plan & Sample size:	The assessment of safety will be based on the safety collective and mainly on the frequency of adverse events and on the observation of clinically significant abnormalities of laboratory values as well as additional safety data (e.g., vital signs, pain by FPS-R, etc).
	PK parameters will be presented in summary tables including sample size, mean, SD, median, minimum and maximum values. Graphical presentation will be produced presenting the calculated AUC for each subject, a summary PK profile for all subjects, and summary PK profiles according to age groups and % TBSA treated.
	Antibodies presence will be determined based on a three-tiered approach analysis of plasma samples drawn prior to start of eschar removal and up to follow up visit at 24 months.
	Sample Size Calculation
	The following sample size calculation is based on the consideration of the primary endpoint of this study.
	Primary Endpoint: Time to Complete eschar removal
	Based on calculated HR (Hazard Ratio) from study MW2004-11-02, for 90% overall power, number per group = 22.

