2.2. Study Objective

The objective of this study is to evaluate the safety and effectiveness of NexoBrid in hospitalized pediatric patients with DPT and FT thermal burns of 1-30% TBSA and to compare NexoBrid to SoC. The specific study objectives are:

- To demonstrate enzymatic eschar removal efficacy of NexoBrid by providing earlier, complete eschar removal,
- To demonstrate enzymatic eschar removal efficacy of NexoBrid by reducing patients' surgical burden, eschar removal related blood loss and resulting in non-inferior final outcomes of cosmesis and function as compared to SoC,
- 3. To assess the safety of NexoBrid compared to SoC.

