7.2.4. Exploratory Analyses

- Incidence of surgical Escharotomy procedures on circumferential extremities target wounds.
- Incidence of reduction in interstitial/compartment pressure in circumferential extremity wounds,
- Reduction in surgical needs as measured by an analysis of % wound area surgically excised for eschar removal.
- Reduction in surgical need as measured by analysis of incidence of surgically harvested donor sites scars,
- Reduction in surgical need as measured by analysis of % area of surgically harvested donor site scars.
- Blood loss related to eschar removal assessed by changes in Hemoglobin incurred during the eschar removal procedures
- PK evaluation in NexoBrid patients
- Cosmesis evaluation (MVSS and POSAS) will be used to assess the quality of the donor site scars,
- Incidence of wound closure
- Additional Cosmesis and Function evaluation will be performed using POSAS measured at 12 and 24 months from wound closure.
- Incidence and extent of Autograft in DPT wounds
- Duration of hospitalization

Statistical Analysis Plan V02 of 31 May 2021

⁴ BOQ will be completed only for patient from study sites in the USA. BOQ₁₁₋₁₈ will be completed by patients aged 11-18. BOQ₀₋₅ will be completed by parents of burned children under the age of 5 years and BOQ₅₋₁₈ will be completed by parents of burned children between the ages of 5 and 18

8. Handling of Protocol Violations

Before database lock and statistical analysis, possible protocol violations will be discussed by data management, sponsor, PI and his/her proxy and the statisticians and classified as minor or major violations. The list with all protocol violations will be prepared by the data management.

A protocol violation will be classified as major if

- The treatment differs from the planned treatment (randomization arm), or
- There was drug misuse (this may include application time deviated in 25% or more, deviation of more than 20% in the TBSA area treated in one session at a time, if relevant, error in drug preparation (e.g. 2g mixed in 50g), storage temperature below 2°C 8°C or >24h at room temperature and used without any stability confirmation by sponsor), or
- treatment started more than 5 days from injury, or
- one of the following inclusion criteria is violated:
 - o Stage 1: Males and females between 4 years to 18 years of age,
 - Stage 2 (upon DSMB review): Males and females between 1 year to 18 years of age,

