All variables not mentioned explicitly in the following will be analyzed descriptively (as part of the case-wise listing).

Unless otherwise specified, all statistical tests will be conducted against a two-sided alternative hypothesis, employing a significance level of 0.05.

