11.1.5.2. Cosmesis and Function at 12 Months from Wound Closure

The MVSS score for a patient will be calculated as described in Section 10.3.4.2. Descriptive statistics of MVSS score at 12 months will be provided by treatment group, for both observed and imputed data (for handling of missing data see Section 10.1.4.2.) The treatment groups will be compared using a linear model with imputed MVSS score at 12 months as the dependent variable. The explanatory variables in the model will include treatment, and the following variables: treatment center, age, %TBSA, proportion of the FT area of a patient and number of TWs (1,2,3-4, ≥5). The coefficient corresponding to the treatment group will be estimated and will represent the estimated mean difference in MVSS score at 12 months between NexoBrid and SoC adjusted for any imbalance in the stratification factors. The results of the regression analysis will be provided.

A clinically meaningful difference will be incorporated into the analysis that will represent a 1.9 or more units advantage to the SoC group, so that the analysis will show whether the NexoBrid group is estimated to have on average a MVSS score that is not worse by more than 1.9 units than the score for the SoC group. That is, the following hypothesis are about to be tested:

$$H_0$$
: $\Delta \ge 1.9$ vs. H_1 : $\Delta < 1.9$

Where Δ is the mean difference in MVSS score between NexoBrid and SoC adjusted for any imbalance in the stratification factors. These hypotheses will be tested by comparing the 95% confidence interval for the coefficient of the treatment group from the linear model outlined above to the clinically meaningful difference 1.9. The null hypothesis will be rejected if the upper bound of this interval is smaller than 1.9.

The main analysis will be performed as described above using both on-site and remotely collected evaluations, with missing values imputed as described in SAP Section 10.1.4.2.

In addition, a sensitivity analysis will be performed (similar to the main analysis described above) to explore the possible influence of remotely captured data. For this sensitivity analysis, the remote evaluations will be "corrected", as described in SAP Section 10.5.2.1, and missing values at 12 months will be imputed applying the imputation procedure from SAP Section 10.1.4.2 on observed *on-site* evaluations and "corrected" *remote* evaluations.

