11.2.8. Handling of Multiple Comparisons

Not applicable. All testing done during this second stage analysis is exploratory in nature. So no adjustment for multiplicity is needed.

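### The protocol sets a non-inferiority aim for POSAS at 12 and 24 months, but the SAP plans only a one-way ANOVA of means with no margin or confidence-interval rule, so a non-significant result would not answer the question

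*SAP*

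**What the plan says.** The protocol synopsis, exploratory endpoints 8 and 9, words the POSAS aim as "Demonstrate non-inferiority to SOC in quality of scars of burns using POSAS treated with NexoBrid", once for 12 months and once for 24 months after wound closure.

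The SAP does not repeat that aim. Section 7.2.4 says "Additional Cosmesis and Function evaluation will be performed using POSAS measured at 12 and 24 months from wound closure". Section 11.1.6.7 (6 and 12 weeks, 6 and 12 months) gives descriptive statistics and then the test: "The mean POSAS values between treatment groups will be compared by a one-way analysis of variance". Section 11.2.5.1 has the same sentence for 18 and 24 months. The default in the introductory part of SAP Section 11 is that, unless otherwise specified, "all statistical tests will be conducted against a two-sided alternative hypothesis, employing a significance level of 0.05".

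For the other scar scale, MVSS, the SAP is fully specified at 12 and 24 months (Sections 11.1.5.2 and 11.2.4.3). It states a null hypothesis that NexoBrid is worse by 1.9 units or more. Besides treatment, the linear model contains "treatment center, age, %TBSA, proportion of the FT area of a patient and number of TWs". The decision rule is: "The null hypothesis will be rejected if the upper bound of this interval is smaller than 1.9".

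**The concern.** A one-way ANOVA with two arms tests the null hypothesis of equal means. Non-inferiority needs a different null hypothesis, namely that NexoBrid is worse by at least a stated margin. Failing to reject equality does not reject that null, and with limited numbers it is compatible with a sizeable deficit.

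Followed as written, the SAP would give a p-value for each POSAS visit and no stated way to decide endpoints 8 and 9. SAP Section 2.2 also has an objective of "resulting in non-inferior final outcomes of cosmesis and function as compared to SoC", so a POSAS result is likely to be read alongside that aim. The planned comparison also leaves out the age, %TBSA, FT-proportion and center factors used in the minimization (SAP Sections 11.1.11 and 13.1), which the 12- and 24-month MVSS models include.

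**Working it through.** **Is there a POSAS figure to reproduce?** No. The supplied text has no POSAS sample size, power, SD or margin.

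**Benchmark: the SAP's MVSS non-inferiority sample size (Section 13.3, based on MW2004-11-02).** The formula is n per group = 2(z_α + z_β)²σ² / [q(Δ − d₀)²], with z_α = 1.96, z_β = 1.28, σ = 2.33, Δ = −0.26 and d₀ = 1.9.

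- Numerator: 2 × 3.24² × 2.33² = 113.98. Squared distance to the margin: 2.16² = 4.6656.
- 12 months, q = 0.7: 113.98 / (0.7 × 4.6656) = 34.9, so 35 per group, as stated.
- 24 months, q = 0.5: 113.98 / (0.5 × 4.6656) = 48.9, so 49 per group, as stated.

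The SAP therefore has a working non-inferiority method for scar quality. POSAS has no counterpart.

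**Precision of a POSAS comparison, in SD units.** Inputs: 145 patients enrolled (SAP Section 13.3); equal arms (assumed); missing data of 0%, or the 30% and 50% that Section 13.3 assumes for MVSS at 12 and 24 months. Carrying those rates over to POSAS is an assumption. Half-width = 1.96 × √(2/n), with n per arm. If the observed difference is just short of significance against NexoBrid, it equals about one half-width, so the upper limit is about twice the half-width.

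| Missing | n per arm | Half-width (SD) | Upper limit, result just short of significance (SD) |
|---|---|---|---|
| 0% | 145/2 = 72.5 | 1.96 × √(2/72.5) = 0.33 | 0.65 |
| 30% | 0.7 × 72.5 = 50.75 | 1.96 × √(2/50.75) = 0.39 | 0.78 |
| 50% | 0.5 × 72.5 = 36.25 | 1.96 × √(2/36.25) = 0.46 | 0.92 |

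The upper limits are doubled before rounding. They are the extreme among non-significant results, not the typical case.

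**How often would the ANOVA be non-significant if NexoBrid were truly worse by exactly the margin?** For two groups F = t², so the probability comes from the noncentral t distribution with 2n − 2 degrees of freedom and noncentrality m√(n/2), two-sided 0.05. The margins m are assumed.

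| Evaluable in total | m = 0.2 SD | 0.3 SD | 0.5 SD | 0.8 SD |
|---|---|---|---|---|
| 145 | 0.78 | 0.57 | 0.15 | 0.002 |
| 101 | 0.83 | 0.68 | 0.30 | 0.02 |
| 72 | 0.87 | 0.76 | 0.45 | 0.08 |

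Comparing the upper bound of a two-sided 95% CI with the margin would hold this error at 0.025.

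**The case against.** The best case for the plan is that the SAP never claims POSAS non-inferiority. It calls POSAS an additional evaluation, and an ANOVA fits that. The cosmesis objective in Section 2.2 is served by MVSS. POSAS is outside the testing hierarchy (Section 11.1.9), and for the second stage Section 11.2.8 says "All testing done during this second stage analysis is exploratory in nature". All of this stands and sets the weight of the point. It does not reconcile the SAP with endpoints 8 and 9. The SAP flags other departures from the protocol (Sections 10.1.3.1, 10.1.3.4 and 10.1.4.2), but not this one.

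A reader might infer more than the documents support, in four ways.

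- *That the planned analysis cannot show non-inferiority at all.* This goes too far. A significant result favouring NexoBrid would imply it. Section 10.3 also plans means and SDs per group, from which an unadjusted interval can be worked out. What is missing is the margin and the rule.
- *That no POSAS margin exists.* The supplied protocol is a synopsis of version 11.01, whereas SAP Section 2.3 refers to version 10.01. The protocol body was not available, so the absence can be stated only for the supplied text.
- *That the sponsor intends to read p > 0.05 as not worse.* No passage says so.
- *That the lack of covariates is what defeats the test.* It is a separate and lesser matter. Unadjusted one-way ANOVA is the SAP's usual choice for continuous exploratory endpoints, including MVSS at 6 weeks, 12 weeks, 6 months and 18 months (Sections 11.1.6.8 and 11.2.5.2).

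The size also depends on the margin. The MVSS margin is 1.9/2.33 = 0.82 SD on the MW2004-11-02 SD. Against a margin that wide, the worst non-significant result would fall inside with 0% or 30% missing (0.65, 0.78) and outside with 50% missing (0.92). Nothing in the documents carries that margin over to POSAS.

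**Conclusion.** The mismatch is real and present at both time points. The synopsis asks whether POSAS scar quality is non-inferior. The SAP tests whether the means differ, and the supplied documents give no margin or interval rule linking the two. A non-significant ANOVA would leave endpoints 8 and 9 unanswered.

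With 145 patients, equal arms and 0% to 50% missing, a non-significant result could coexist with an upper limit of about 0.65 to 0.92 SD against NexoBrid. These figures rest on assumed missing-data rates and cannot be converted to score points, because no POSAS SD is given. Priority is low: POSAS is exploratory, and MVSS carries the formal scar-quality test.

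**What to change.** 1. For POSAS at 12 and 24 months, fit the linear model specified for MVSS (treatment, center group, age, %TBSA, FT proportion, number of TWs) and report the NexoBrid minus SoC difference with its 95% CI. Use the observed POSAS scores, in line with SAP Section 10.5.2.3. The MVSS model uses imputed scores, and that step should not be copied without a decision to do so. State which direction of the score is worse, since SAP Sections 10.1.5.1 and 10.3.5.7 do not.
2. Claim non-inferiority only if a justified POSAS margin is fixed before the relevant database lock, and judge it by comparing the limit of the 95% CI with that margin.
3. Otherwise reword endpoints 8 and 9 as estimation of the difference, and state in the SAP that a non-significant test is not evidence of non-inferiority.

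The cost is small: two extra model fits, a change of SAP wording, and a protocol wording change if the endpoints are reworded. The MVSS specification can be reused, with the outcome and the missing-data step changed. No new data are needed.

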11.1.6.8. MVSS (target wounds)

The MVSS for target wounds (analyzed on a subject level) at 6 and 12 weeks and 6 months (both on-site and remotely collected) will be calculated as outlined in Section 10.3.4.2 and will be presented by treatment group using descriptive statistics. The mean MVSS values between treatment groups will be compared by a one-way analysis of variance.

In addition, the analysis will be repeated excluding subjects with remotely collected data.

11.1.6.9. Duration of hospitalization

The duration of hospitalization will be analyzed descriptively with Kaplan-Meier plots and compared between groups with a log rank test.

11.1.7. Pharmacokinetic Variables

Pharmacokinetic variables will be analyzed separately. The analysis is described in a separate document.

11.1.8. Multicenter Data

Randomization will be stratified by center as detailed in the Section 15.7.2 of the protocol.

The analyses of the primary and secondary endpoints of this trial will adjust for possible center effects by including the grouped center as covariate in the analyses. The grouping will be done using the geographical regions: US (United States), EEU (Eastern Europe), WEU (Western Europe) and India.

11.1.9. Handling of Multiple Comparisons

Unless otherwise specified, all statistical tests will be conducted against a two-sided alternative hypothesis, employing a significance level of 0.05. The primary and secondary endpoints of efficacy will be tested in a hierarchy, so as to preserve the nominal significance levels:

- 1. Primary: time to complete eschar removal
- 2. Secondary: Incidence of surgical excision
- 3. Secondary: Blood loss
- 4. Secondary: Area of Autograft in DPT wounds

5. Secondary: Incidence of Autograft in DPT wounds

11.1.10. Interim Analysis

No interim analyses will be performed.

11.1.11. Stratification

The following factors are used to stratify the study design:

A. Age group:

A1: 0 to 23 month

A2: 24 months to 3 years

A3: 4 to 11 years

A4: 12 to 18 years

B. Overall total area of burns measured by % of TBSA

B1: (1% to 15%), inclusive

B2: (> 15% to \leq 30%)

C. The proportion of the FT area out of the total burned area of a patient

C1: < 20% of the burned area defined as FT

C2: ≥ 20% of the burned area defined as FT

D. Clinical center, so as to address possible differences in SoC procedures between sites (if any), to allow comparison of the results within center and to reduce the likelihood of a center including patients in only one arm of the study.

 $D_1, D_2,...,D_m$ (m being the number of participating clinical centers).

Using this stratification, patients will be randomized in a 1:1 ratio (NexoBrid: SoC).

11.1.12. Analysis of Subgroups

The following subgroup analyses were pre planned and will be conducted to explore efficacy and safety within certain pre-defined subgroups of the population. All analyses presented here are of exploratory nature.

11.1.12.1. Age group 0-23 months

A subgroup analysis will be performed on the subject aged 0-23 months.

The primary endpoint time to eschar removal will be analyzed with Kaplan-Meier curves to display the distribution of time to complete eschar removal under the two treatments. Time to complete eschar removal will be compared between treatment groups by a log rank test.

For the secondary endpoint "incidence of surgical excision" counts and percentages of patients needing surgical excision will be presented. The treatment groups will be compared using a chi square test (of Fisher's exact test in case of small expected cell counts).

For the secondary endpoint "blood loss" descriptive statistics will be presented by treatment group. Treatment groups will be compared using a t-test.

For the secondary endpoint "area of Autograft in DPT wounds" descriptive statistics (on a subject level) will be presented by treatment group. Treatment groups will be compared using at-test.

For the secondary endpoint "incidence of Autograft in DPT wounds" counts and percentages on a target wound level will be presented by treatment group. The treatment groups will be compared using a logistic regression within the generalized estimating equations (GEE) framework that accounts for within-subject correlation between target wounds.

The analysis of Adverse Events for the sub-period until the 12 weeks follow-up, (see Section 11.1.5.4) will be repeated, as deemed relevant, on the subgroup of patients aged 0-23 months.

The analyses of PTT/INR (see Section 11.1.5.14) will be repeated on the subgroup of patients aged 0-23 months.

The analyses of central laboratory parameters (see Section 11.1.5.5) will be repeated, as deemed relevant, on the subgroup of patients aged 0-23 months. The following parameters will be analyzed:

- Biochemistry: Creatinine, Glucose, Total Bilirubin, Albumin, Calcium (Ca++), Sodium (Na+), Potassium (K+), Alkaline Phosphatase, SGOT (ASAT), SGPT (ALAT), LDH.
- Hematology: Hemoglobin, Hematocrit, Platelets, Total WBC, Neutrophils, Lymphocytes.

The same analyses as outlined in Section 11.1.12.1 will be performed but on the subgroup of patients aged 24 months – 3 years.

The same analyses as outlined in Section 11.1.12.1 will be performed but on the subgroup of patients aged 0 - 3 years.

The same analyses as outlined in Section 11.1.12.1 will be performed but on the subgroup of patients aged 4 - 11 years.

The same analyses as outlined in Section 11.1.12.1 will be performed but on the subgroup of patients aged 12 – 18 years

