9.1.1. Primary Endpoint: Time to Complete Eschar Removal

Estimated log hazard ratio from study MW2004-11-02 (SoC versus NexoBrid) = -1.39, using a Cox proportional hazards model with treatment as only covariate.

Standard error = 0.28

Target log hazard ratio = -1.39 + 0.28/2 = -1.25; target hazard ratio $\lambda = 0.29$.

The formula for the number of events D (successful complete eschar removals) is:

$$D = \frac{4(z_{\alpha} + z_{\beta})^2}{(\ln \lambda)^2}$$

(Piantadosi, Clinical Trials: A Methodologic Perspective, p.169)

 $z_{\alpha} = 1.96$;

 z_{β} = 1.28 for 90% power.

If the proportion of events in NexoBrid group is denoted by $p_1 = 0.59$

and the proportion of events in SoC group is denoted by $p_2 = 0.70$,

which are the observed proportions in the study MW2004-11-02, the number of patients required $n = \frac{2D}{p_1 + p_2} = 42$ (to the nearest even number), 21 in each group.

In accordance with the European regulatory requests and planned age distribution, we believe that a sample size of 80 patients per arm will detect with a 90% power a difference on the primary endpoint, which is well within what would be expected, based on the results from the previous study.

Based on the above calculations, we plan a study with total sample size of 160 patients; 80 (NexoBrid) + 80 (SoC)⁵.

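### The age subgroups are explored only by separate within-band tests, so the planned output cannot show whether the treatment effect differs by age

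*SAP*

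**What the plan says.** SAP 11.1.12.1 sets out the analyses for ages 0-23 months, and 11.1.12.2 to 11.1.12.5 repeat them for 24 months-3 years, 0-3 years pooled, 4-11 years and 12-18 years. For time to complete eschar removal there are Kaplan-Meier curves, and "Time to complete eschar removal will be compared between treatment groups by a log rank test". The secondary endpoints get counts or descriptive statistics by arm, with a chi-square or Fisher test, t-tests, or a GEE logistic regression.

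The opening of 11.1.12 calls these analyses pre-planned and exploratory. It sets no success rule for any band. Under SAP section 11 the default is that "all statistical tests will be conducted against a two-sided alternative hypothesis, employing a significance level of 0.05".

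No treatment-by-age interaction appears in the SAP text supplied. The only interaction terms there are with time, to check proportional hazards (11.1.3 and 11.1.5.1). For the primary endpoint, 11.1.12 names no subgroup hazard ratio and no confidence interval.

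The protocol synopsis (Statistical Plan & Sample size) bases the subgroup analyses on "Age groups (Comparison of 0-23 months; 24 months-3 years; 4-11 years; 12-18 years" and gives no method.

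**The concern.** Whether the effect is similar across ages matters in this trial. Enrolment was opened by age in three stages, the planned age distribution was one stated reason for going to 80 patients per arm, and age is a minimization factor.

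A significant result in one band and a non-significant result in another is not evidence that the effects differ. With bands of 20 to 50 patients, the p-values largely reflect band size. A clinical reader given only a p-value and a pair of curves for the 20 adolescents could take p≥0.05 as absence of effect at that age, even when the estimate agrees with the other bands. What is at stake is how the subgroup tables are read; the primary test is not touched.

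**Working it through.** **Inputs**
- Planning effect (SAP 9.1.1): "Target log hazard ratio = -1.39 + 0.28/2 = -1.25; target hazard ratio" of 0.29. Only the absolute size matters here. The rounded HR gives |ln 0.29| = 1.238, so both 1.25 and 1.238 are carried.
- Event proportions (SAP 9.1.1): 0.59 and 0.70, mean (0.59 + 0.70)/2 = 0.645.
- Two-sided 5%, z = 1.96; for the design, z = "1.28 for 90% power".
- Allocation (SAP 11.1.11): "patients will be randomized in a 1:1 ratio (NexoBrid: SoC").
- Enrolled by age (SAP 13.3): 45, 30, 50, 20.

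**The plan's own figure**

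D = 4(1.96 + 1.28)²/1.25² = 41.99/1.5625 = 26.9 events; n = 2 × 26.9/1.29 = 41.7, so 42. This matches the SAP's 42 (21 per group). The documents give no power for any age band.

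**Power per band under one common effect**

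The same formula, solved for power: Φ(√(0.645 n)/2 × |log HR| − 1.96).

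| Band | n | Expected events | Power, 1.25 | Power, HR 0.29 |
|---|---|---|---|---|
| 0-23 months | 45 | 29.0 | 92.0% | 91.5% |
| 24 months-3 years | 30 | 19.4 | 78.5% | 77.7% |
| 4-11 years | 50 | 32.3 | 94.4% | 94.0% |
| 12-18 years | 20 | 12.9 | 61.2% | 60.4% |

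The four bands share no patients, so the powers multiply. At 1.25, 1 − 0.920 × 0.785 × 0.944 × 0.612 = 0.58. At HR 0.29 it is 0.60. The pooled 0-3 years band (75 patients, power about 99%) overlaps the first two and is left out of the product.

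**Sensitivity: chance that at least one band has p≥0.05**
- Unshrunk log HR 1.39 (SAP 9.1.1), event share 0.645: 43%.
- Higher event shares (assumed; not in the documents), at 1.25 and HR 0.29 respectively: 43-44% at 0.80, 34-36% at 0.90, 27-29% if all children have the event. The figure drops below 50% at a share of about 0.73-0.74.
- Freedman formula, Φ(√events × (1 − HR)/(1 + HR) − 1.96), HR 0.29: powers 84%, 68%, 88%, 51%; 75%.
- Simulated log-rank test with event proportions 0.59 and 0.70: powers 83%, 65%, 87%, 47%; 78%.
- SAP 13.3's second scenario, in which proportional hazards was rejected and 94 patients give 90% power: 94%. This treats the log-rank test as behaving like the Wilcoxon-Gehan test, so it is indicative only.

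**Surgical excision, same question**

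Fisher's exact test with 22, 15, 25 and 10 per arm. At the SAP 9.1.2 proportions of 0.44 and 0.78, power is 53%, 31%, 63% and 17%, so at least one band is non-significant 98% of the time. At the 0.05 and 0.70 taken from the later study (SAP 13.3), the figure is 22%.

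**What estimates and an interaction test would give**

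With SE = 2/√events and HR 0.29 in every band, the approximate 95% CIs are 0.14-0.60, 0.12-0.71, 0.15-0.58 and 0.10-0.86. They overlap heavily, which shows consistency more directly than four p-values do. A 3-df heterogeneity test at 5% would signal a difference 5% of the time under a common effect. Its non-centrality is Σ(events/4)(β − β̄)². With no effect at 12-18 years this is 4.26, giving 38% power; with no effect at 24 months-3 years it is 5.88, giving 51%.

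**The case against.** The SAP labels these analyses exploratory, no subgroup stands in the hierarchy of 11.1.9, and no band has to reach significance. That stands. A reader might infer that a uniform effect would probably "fail" in some age group. The documents do not support this: they contain no pass/fail rule, and missing p<0.05 is not an estimate in the wrong direction. "Probably" also holds only at the planning inputs, which come from an earlier study that mixed adults and children.

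A reader might also infer that the protocol promised a comparison across ages and the SAP dropped it. The synopsis wording can equally mean comparing treatments within each age group, and the protocol's full statistical section is not among the supplied documents. This cannot be settled.

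The planned output is more than p-values. Curves, counts and descriptive statistics by arm let a reader judge direction and rough size, and the pooled 0-3 years band eases the problem for the 30-patient group. This narrows the point but does not remove it: for the primary endpoint nothing planned gives an age-specific effect estimate with its uncertainty, or compares those estimates. Calling the analyses exploratory does not supply that comparison, and nominal p-values are still planned.

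Finally, an interaction test is itself weak here, and a null result could be misread as proof of consistency. That stands and limits what the fix can claim.

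**Conclusion.** The point holds as a cheap improvement to an exploratory analysis. As written, SAP 11.1.12 cannot show whether the treatment effect differs by age. At the SAP's planning values, a common effect would leave at least one of four bands non-significant about 58-60% of the time. That rests on a target log HR of about 1.25, a mean event share of 0.645 and roughly equal arms within each band. The figure should be quoted with those assumptions and its range, about 27% to 78% across the inputs and methods above (leaving aside the indicative Wilcoxon-Gehan scenario). Most of it comes from the 20-patient band, which alone has a 39-40% chance of p≥0.05. The primary analysis and the testing hierarchy are unaffected.

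**What to change.** - Leave the primary Cox model unchanged. Adding an interaction to it would turn its treatment coefficient into the effect in one reference age group and so alter the primary test.
- Add a separate exploratory Cox model for time to complete eschar removal with age group (four levels), treatment and their 3-df interaction. Do the same with a logistic model for surgical excision.
- Report the hazard or odds ratio with 95% CI for each age band in a forest plot, next to the interaction result.
- Report median time to eschar removal with its CI by arm and band. SAP 11.1.3 replaces the Cox model with a Wilcoxon-Gehan test if proportional hazards is rejected, and SAP 13.3 says it was rejected in the second phase 3 study.
- Drop the within-band p-values, or mark them as not for inference.
- State beside the result that the interaction test has low power (about 38-51% even if one of the two smaller bands had no effect), so that a non-significant result is not read as proof of consistency.

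The cost is two further models and a figure, from data already collected.
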